7.7.3 Analysis of Secondary and Exploratory Endpoints

The frequency and severity of adverse events following ^{11}C -YJH08 injection will be descriptively reported, using CTCAE v 5.0. Organ dosimetry on PET will be calculated using standard technique.

The median and range for intra-tumoral SUV_{max} within metastatic lesions will be descriptively reported to asses for intra-tumoral heterogeneity and differences in uptake by site of disease.

For the purposes of analyzing the association between baseline and percent change from baseline in $\text{SUV}_{\text{max-ave}}$ with subsequent clinical outcomes, the cohort will be dichotomized above and below the median for the study cohort. The PSA response rate (PCWG3 criteria; Cohort B only), clinical benefit rate, and objective response rate (in subset of measurable tumors by RECIST 1.1) will be compared between dichotomized groups using the chi-squared test. The

log rank test will be used to compare progression-free survival between dichotomized subgroups.

For patients who undergo optional tumor biopsy with evaluable tumor content, the correlation between SUV_{max} of the target lesion on PET with GR expression by IHC (using H-score method) will be computed using Pearson correlation method. Likewise, the correlation between SUV_{max} on PET with GR transcriptional signature activity by RNA-seq will be determined using Pearson correlation method when sufficient tumor content permits transcriptional analysis.

No adjustment will be made for multiple comparisons for the analysis of the secondary and exploratory endpoints.

8 Study Management

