2.2 Primary Objectives

Primary Objective	Endpoint(s)	Time Frame
1. Cohort A: To determine the feasibility of metastatic lesion detection in using ^{11}C -YJH08 PET.	Cohort A: Sensitivity of metastatic lesion detection in using ^{11}C -YJH08 PET.	2 days
2. Cohort B and C: To determine the mean percent change from baseline at the time of progression on systemic therapy in $\text{SUV}_{\text{max-ave}}$ on paired ^{11}C -YJH08 PET on a per-patient and per-lesion basis.	Cohort B and C: Mean percent change from baseline at the time of progression on systemic therapy in $\text{SUV}_{\text{max-ave}}$ on paired ^{11}C -YJH08 PET on a per-patient and per-lesion basis.	Baseline to time of progression

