2.3 Secondary Objectives

Secondary Objective	Endpoint(s)	Time Frame
1. To determine the safety and determine average organ uptake of ¹¹ C-YJH08.	Safety as recorded by CTCAE v 5.0 criteria and organ dosimetry of ¹¹ C-YJH08 PET.	2 days
2. To descriptively report the patterns of intra-tumoral uptake of ¹¹ C-YJH08 on whole body PET, including by site of disease, uptake by tumor type, inter-tumoral and inter-patient heterogeneity, and tumor-to-background signal.	Descriptive patterns of intra-tumoral uptake of ¹¹ C-YJH08 on whole body PET, including by site of disease, uptake by tumor type, inter-tumoral and inter-patient heterogeneity, and tumor-to-background signal will be assessed.	2 days
3. Cohort B and C: To determine whether baseline uptake on ¹¹ C-YJH08 PET is associated with subsequent clinical outcomes including objective response rate, progression-free survival, and PSA50 response.	Association between baseline uptake on ¹¹ C-YJH08 PET with subsequent clinical outcomes including objective response rate, progression-free survival, and PSA50 response	Baseline to time of progression.

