5.2.3 OPTIONAL ^{11}C -YJH08 PET at Progression (Cohorts B and C)

Patients will undergo optional repeat ^{11}C -YJH08 PET at the time of progression by PCWG3 criteria for Cohort B and RECIST 1.1 criteria for Cohort C. Patients who underwent PET/CT at baseline should have same imaging modality performed during follow-up, and likewise patients who underwent PET/MR at baseline should have same imaging modality performed during follow up.

- Vital Signs
- Concomitant medication review

Period/ Procedure	Screening (Day -28 thru C1D1)	Cycle 1, Day 1 (Baseline PET)	Disease Progression (Cohort B and C)
Study / Investigational Product Administration			
¹¹ C-YJH08 PET		X	X
Administrative Procedures			
Informed consent	X		
Clinical Assessments			
Baseline conditions	X		
Vital signs ¹	X	X	X
Concomitant medications	X		X
AE assessment ²	X	X	
Demographics	X		
Performance status	X		
Laboratory Assessments			
Serum creatinine, total bilirubin, AST, ALT, CBC + diff ³	X	X	
PSA, Serum Testosterone	X		
Imaging Procedures			
Staging scans (CT or MRI)	X		
ECG/EKG		X ⁴	
Tissue Collection/ Biopsy			
Tumor biopsy (optional) ⁵		X	

¹ Vital signs (blood pressure, heart rate) will be collected at screening, before and after administration of ¹¹C-YJH08 injection, then at 60 minutes (+/- 15 min), and 2 hours (+/- 30 min) following ¹¹C-YJH08 injection.

² Safety monitoring will include adverse event assessment at screening, 60 minutes (+/- 15 min), 2 hours (+/- 30 min) and 24 hours (+/- 4 hours) following ¹¹C-YJH08 injection.

³ Serum creatinine, total bilirubin, AST, ALT, and CBC + diff will be performed at screening and at 24 hours (+/- 4 hours) following ¹¹C-YJH08 injection.

⁴ EKG will be performed prior to ¹¹C-YJH08 injection and at 2 hours (+/- 30 min) following ¹¹C-YJH08 injection.

⁵ Metastatic tumor biopsy is optional. Tumor biopsy should be performed within 14 days following baseline PET. Soft tissue, PET-avid lesions should be prioritized for biopsy whenever feasible.

Supportive Care

Subjects will receive full supportive care as medically indicated.

The Principal Investigator or designee will be present during the administration and monitoring period. Any events occurring during or subsequent to the administration of IMP will be addressed as required by the monitoring nurse and/or physician as deemed appropriate.

6 Reporting and Documentation of Results

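### Section 7.7.3 tests percent change in SUVmax-ave against subsequent PFS and response, although that change is first known at the optional PET done at progression

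*Combined protocol and SAP*

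**What the plan says.** Section 7.7.3 takes two explanatory measures from SUVmax-ave, and its sentence opens "For the purposes of analyzing the association between baseline and percent change from baseline in" that quantity. Both measures are then handled by one rule, a median split set against later outcomes, which the same sentence words as "with subsequent clinical outcomes, the cohort will be dichotomized above and below the median for the study cohort". The resulting groups are compared by chi-squared test on PSA response (Cohort B), clinical benefit and objective response, and by log-rank test on PFS. The section states no PFS origin, landmark or time-dependent method, and makes no multiplicity adjustment.

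Secondary objective 3 (section 2.3) is narrower. It asks whether baseline uptake "is associated with subsequent clinical outcomes including objective response rate, progression-free survival, and PSA50 response", over the time frame "Baseline to time of progression". Percent change appears in neither the objective nor its endpoint.

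Percent change belongs to the primary objective for Cohorts B and C (section 2.2), which concerns the "mean percent change from baseline at the time of progression on systemic therapy in" the per-patient uptake measure. The scan that supplies it is described in section 5.2.3. It is voluntary, as the opening words "Patients will undergo optional repeat" show, and its timing is fixed there as "at the time of progression by PCWG3 criteria for Cohort B and RECIST 1.1 criteria for Cohort C". Disease progression is the last column of the schedule of events. Section 7.7.1 leaves missing values missing.

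**The concern.** A measure can be related to a subsequent outcome only if it is known before that outcome. Baseline uptake is. Percent change is not, if PFS and response run from baseline to progression, because progression is what triggers the second scan.

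Two consequences follow. First, the analysed set is selected on the outcome: everyone with a percent-change value has progressed, and patients who have not progressed or who decline the scan drop out. Second, the interval between scans is the PFS time itself. If uptake tends to rise or fall with time, for any reason, patients with longer PFS show a larger change, and the log-rank test reports an association that carries no prognostic information. Its direction follows the direction of the drift. A reader could take such a result as evidence that a change in tracer uptake predicts PFS.

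**Working it through.** **Order of events.** The plan states no figure to reproduce here, so the first check sets the sections side by side.

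| Item | When it is known | Source |
|---|---|---|
| Baseline SUVmax-ave | Day 1 | 5.2.2 |
| Percent change in SUVmax-ave | At progression, if the optional scan is done | 2.2, 5.2.3 |
| PFS event | At progression | 2.3 (time frame) |
| Response on that therapy | By progression | 2.3 (time frame) |
| Any outcome after the second PET | Not described | Schedule of events |

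The one or two imaging time points in section 5.2.2 belong to the Day 1 session and are not an on-treatment scan. Cohort B's baseline PET is itself done at progression on earlier therapy, but the change is still measured at the later progression.

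**Why drift alone creates an association.** Let T be PFS time and let log change = r·T + e. Here r is a patient's monthly drift, with mean mu and SD s, independent of T, and e is noise with SD v. For exponential T with mean m = median/ln 2:

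- Cov(log change, T) = mu·m²
- Var(log change) = mu²·m² + 2·s²·m² + v²
- correlation = mu·m / sqrt(mu²·m² + 2·s²·m² + v²)

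Example with assumed values (median 6 months, mu = 0.03, s = 0.02, v = 0.2): m = 6/0.693 = 8.66 and m² = 74.9. The numerator is 0.03 × 8.66 = 0.260. The variance is 0.0674 + 0.0599 + 0.04 = 0.167, with square root 0.409. The correlation is 0.260/0.409 = 0.63, although r carries no information about T.

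**Size at the planned sample.** The evaluable number per cohort, 10, comes from section 7.2. Everything else is assumed. Each setting has 40,000 simulated trials (Monte Carlo SE at most 0.25 points), with all patients progressed and rescanned, a median split, and rejection at log-rank |z| > 1.96. Each cell gives the rejection rate for s = 0.02 / 0.03.

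| Median PFS (months), noise v | mu 0 | mu +0.01 | mu +0.03 | mu -0.03 |
|---|---|---|---|---|
| 3, 0.2 | 0.073 / 0.074 | 0.085 / 0.085 | 0.181 / 0.157 | 0.178 / 0.155 |
| 6, 0.2 | 0.078 / 0.085 | 0.105 / 0.100 | 0.298 / 0.227 | 0.300 / 0.225 |
| 10, 0.2 | 0.090 / 0.094 | 0.126 / 0.119 | 0.388 / 0.280 | 0.391 / 0.275 |
| 3, 0.4 | 0.070 / 0.073 | 0.075 / 0.073 | 0.111 / 0.104 | 0.109 / 0.105 |
| 6, 0.4 | 0.073 / 0.078 | 0.086 / 0.085 | 0.183 / 0.157 | 0.180 / 0.153 |
| 10, 0.4 | 0.079 / 0.080 | 0.101 / 0.098 | 0.264 / 0.206 | 0.265 / 0.207 |

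Baseline uptake gives 0.070 to 0.072 in the same setting, so 7% is the small-sample reference rather than 5%. At mu = +0.03, between 0.898 and 0.999 of rejections read as a larger rise going with longer PFS. At mu = -0.03 the direction reverses.

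| Analysed patients | mu 0 | mu +0.01 | mu +0.03 or -0.03 | Baseline uptake |
|---|---|---|---|---|
| 8 (two without a second scan) | 0.055–0.079 | 0.060–0.097 | 0.077–0.288 | 0.057–0.059 |
| 20 (cohorts pooled) | 0.064–0.089 | 0.075–0.167 | 0.141–0.646 | 0.064–0.065 |

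A simpler model agrees in kind: mean PFS 6 months, the same drift in every patient, and noise SD 30 percentage points. At n = 10 it rejects 7%, 17%, 35% and 66% of the time at drifts of 0, 2.5, 5 and 10 points per month.

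**Response outcomes.** Response was linked to PFS by logit P = -0.6 + b·log(T/median), with b from 1 to 2. At n = 10 the uncorrected chi-squared test rejects in 0.062–0.073 of trials at mu 0, 0.065–0.087 at +0.01 and 0.076–0.188 at +0.03 or -0.03. When response is unrelated to PFS (b = 0) it rejects in 0.058–0.064. With a continuity correction the rate is at most 0.012. The plan does not say which version it uses.

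**The case against.** The strongest reply is that the schedule proves less than it seems to. After baseline it lists no staging scans or PSA at all, so the outcomes of the baseline-uptake analysis are not scheduled either, and silence cannot exclude outcomes on a later therapy. The time frame is also taken from objective 3, which does not cover percent change. On this view the plan is ambiguous about the PFS origin rather than wrong. The schedule point is fair, and outcomes on a next therapy would be correctly ordered. But the plan describes no such origin or follow-up, and the only time frame attached to these outcomes ends at progression. Followed as written, the rule relates PFS to a value measured at its own endpoint.

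Two further points stand in part. Section 7.7.3 speaks of association, and a chi-squared test does not need the change to come first. For response the fault is therefore mainly one of order and of the word *subsequent*, and the inflation is small unless drift is large. The high rejection rates also need a systematic drift of 3% per month, and the extremes need long PFS and low noise as well. With no mean drift the excess at n = 10 is about 2 points. These limits bear on how much weight the point deserves, not on whether the order is wrong.

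**Conclusion.** The percent-change part of the association analysis is wrong as written. On the baseline-to-progression time frame, percent change cannot predict PFS or response, and it goes beyond secondary objective 3. This rests on the documents alone and needs no simulation.

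The size of the resulting error cannot be known from the documents, which give no drift, noise or PFS figures. Under the assumptions above, false rejection in one cohort of 10 runs from close to the 7% reference at zero mean drift to 39% at 3% per month. Without the mildest corner (median PFS 3 months with noise 0.4), the range at +3% or -3% is 15% to 39%.

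The change should be made, but the stakes are limited. One unadjusted secondary analysis is affected. The baseline-uptake analysis, the primary endpoints, the decision to proceed beyond Cohort A and the safety rule do not depend on it.

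**What to change.** Reword the sentence in section 7.7.3 so that baseline uptake is the only grouping variable, for example: *Patients will be split at the cohort median of baseline SUVmax-ave, and the two groups compared on later clinical outcomes.* The log-rank and chi-squared comparisons then match the predictor in section 2.3.

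Keep the reporting of percent change in section 7.7.2, where it is already planned. If it is shown against response or time to progression, label that display descriptive, with no test and no predictive claim.

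This costs wording and one secondary comparison; scans, visits and sample size are unchanged. If the sponsor does want to study what follows a change in uptake, the plan would need an outcome with its time origin at the second PET and follow-up added to the schedule, which is a larger change.

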8.1 Pre-study Documentation

This study will be conducted in accordance with the ethical principles that have their origin in the Declaration of Helsinki as stated in 21 CFR §312.120(c)(4); consistent with GCP and all applicable regulatory requirements.

Before initiating this trial, the Investigator will have written and dated approval from the Institutional Review Board for the protocol, written informed consent form, subject recruitment materials, and any other written information to be provided to subjects before any protocol related procedures are performed on any subjects.

The Investigator must comply with the applicable regulations in Title 21 of the Code of Federal Regulations (21 CFR §50, §54, and §312), GCP/ICH guidelines, and all applicable regulatory requirements. The IRB must comply with the regulations in 21 CFR §56 and applicable regulatory requirements.

The clinical investigation will not begin until either FDA has determined that the study under the Investigational Drug Application (IND) is allowed to proceed, or the Investigator has received a letter from FDA stating that the study is exempt from IND requirements.

8.2 Institutional Review Board Approval

The protocol, the proposed informed consent form, and all forms of participant information related to the study (e.g. advertisements used to recruit participants) will be reviewed and approved by the UCSF IRB. Prior to obtaining IRB approval, the protocol must be approved by the Helen Diller Family Comprehensive Cancer Center Site Committee and by the Protocol Review Committee (PRC). The initial protocol and all protocol amendments must be approved by the IRB prior to implementation.

8.3 Informed Consent

All participants must be provided a consent form describing the study with sufficient information for each participant to make an informed decision regarding their participation. Participants must sign the IRB-approved informed consent form prior to participation in any study specific procedure. The participant must receive a copy of the signed and dated consent document. The original signed copy of the consent document must be retained in the medical record or research file.

8.4 Changes in the Protocol

Once the protocol has been approved by the UCSF IRB, any changes to the protocol must be documented in the form of an amendment. The amendment must be signed by the Investigator and approved by PRC and the IRB prior to implementation.

If it becomes necessary to alter the protocol to eliminate an immediate hazard to patients, an amendment may be implemented prior to IRB approval. In this circumstance, however, the Investigator must then notify the IRB according to institutional requirements.

8.5 Handling and Documentation of Clinical Supplies

The Principal Investigator will maintain complete records showing the receipt, dispensation, return, or other disposition of all investigational drugs. The date, quantity and batch or code number of the drug, and the identification of patients to whom IMP has been dispensed by patient number and initials will be included. The sponsor- investigator will maintain written records of any disposition of the IMP.

The Principal Investigator shall not make the investigational drug available to any individuals other than to qualified study patients. Furthermore, the Principal Investigator will not allow the investigational drug to be used in any manner other than that specified in this protocol.

8.6 Case Report Forms (CRFs)

The Principal Investigator and/or his/her designee will prepare and maintain adequate and accurate participant case histories with observations and data pertinent to the study. Study specific Case Report Forms (CRFs) will document safety and treatment outcomes for safety monitoring and data analysis. The Clinical Research Coordinator (CRC) will complete the CRFs as soon as possible upon completion of the study visit; the Investigator will review and approve the completed CRFs.

The information collected on CRFs shall be identical to that appearing in original source documents. Source documents will be found in the patient's medical records maintained by UCSF personnel. All source documentation should be kept in separate research folders for each patient.

In accordance with federal regulations, the Principal Investigator is responsible for the accuracy and authenticity of all clinical and laboratory data entered onto CRFs. The PI will approve all completed CRFs to attest that the information contained on the CRFs is true and accurate.

The Principal Investigator will be responsible for ensuring the accurate capture of study data. At study completion, when the CRFs have been declared to be complete and accurate, the database will be locked. Any changes to the data entered into the CRFs after that time can only be made by joint written agreement among the Study Chair, the Trial Statistician, and the Protocol Project Manager.

All source documentation and CTMS data will be available for review/monitoring by the UCSF DSMC and regulatory agencies.

8.7 Oversight and Monitoring Plan

The UCSF Helen Diller Family Comprehensive Cancer Center DSMC will be the monitoring entity for this study. The UCSF DSMC will monitor the study in accordance with the NCI-approved Data and Safety Monitoring Plan (DSMP). The DSMC will routinely review all adverse events and suspected adverse reactions considered "serious". The DSMC will audit study-

related activities to ensure that the study is conducted in accordance with the protocol, local standard operating procedures, FDA regulations, and Good Clinical Practice (GCP). Significant results of the DSMC audit will be communicated to the IRB and the appropriate regulatory authorities at the time of continuing review, or in an expedited fashion, as applicable. Appendix 2 – Data and Safety Monitoring Plan.

8.8 Record Keeping and Record Retention

The Principal Investigator is required to maintain adequate records of the disposition of the drug, including dates, quantity, and use by subjects, as well as written records of the disposition of the drug when the study ends.

The Principal Investigator is required to prepare and maintain adequate and accurate case histories that record all observations and other data pertinent to the investigation on each individual administered the investigational drug or employed as a control in the investigation. Case histories include the case report forms and supporting data including, for example, signed and dated consent forms and medical records including, for example, progress notes of the physician, the individual's hospital chart(s), and the nurses' notes. The case history for each individual shall document that informed consent was obtained prior to participation in the study.

Study documentation includes all CRFs, data correction forms or queries, source documents, Sponsor-Investigator correspondence, monitoring logs/letters, and regulatory documents (e.g., protocol and amendments, IRB correspondence and approval, signed patient consent forms).

Source documents include all recordings of observations or notations of clinical activities and all reports and records necessary for the evaluation and reconstruction of the clinical research study.

In accordance with FDA regulations, the Principal Investigator shall retain records for a period of 2 years following the date a marketing application is approved for the drug for the indication for which it is being investigated; or, if no application is to be filed or if the application is not approved for such indication, until 2 years after the investigation is discontinued and FDA is notified.

9 References

1. Boudadi, K. & Antonarakis, E. S. Resistance to Novel Antiandrogen Therapies in Metastatic Castration-Resistant Prostate Cancer. *Clinical Medicine Insights. Oncology* **10**, 1-9, doi:10.4137/CMO.S34534 (2016).
2. Arora, V. K. *et al.* Glucocorticoid receptor confers resistance to antiandrogens by bypassing androgen receptor blockade. *Cell* **155**, 1309-1322, doi:10.1016/j.cell.2013.11.012 (2013).
3. Li, J. *et al.* Aberrant corticosteroid metabolism in tumor cells enables GR takeover in enzalutamide resistant prostate cancer. *eLife* **6**, doi:10.7554/eLife.20183 (2017).

Appendix 1 Performance Status Criteria

ECOG Performance Status Scale		Karnofsky Performance Scale	
Grade	Descriptions	Percent	Description
0	Normal activity Fully active, able to carry on all pre-disease performance without restriction	100	Normal, no complaints, no evidence of disease
		90	Able to carry on normal activity; minor signs or symptoms of disease
1	Symptoms, but ambulatory Restricted in physically strenuous activity, but ambulatory and able to carry out work of a light or sedentary nature (e.g., light housework, office work)	80	Normal activity with effort; some signs or symptoms of disease
		70	Cares for self, unable to carry on normal activity or to do active work
2	In bed < 50% of the time Ambulatory and capable of all self-care, but unable to carry out any work activities Up and about more than 50% of waking hours	60	Requires occasional assistance, but is able to care for most of his/her needs
		50	Requires considerable assistance and frequent medical care
3	In bed > 50% of the time Capable of only limited self-care, confined to bed or chair more than 50% of waking hours	40	Disabled, requires special care and assistance
		30	Severely disabled, hospitalization indicated Death not imminent
4	100% bedridden Completely disabled Cannot carry on any self-care Totally confined to bed or chair	20	Very sick, hospitalization indicated Death not imminent
		10	Moribund, fatal processes progressing rapidly
5	Dead	0	Dead

